4.3. Reproductive Risks

Nintedanib can cause harm to developing fetus. For this reason, males and females of childbearing potential will be counseled on the need to use adequate contraception (eg, oral contraceptives, intrauterine devices, barrier methods) for all sexual encounters prior to start of study therapy and for at least 3 months following discontinuation of study therapy.

Female subjects will be considered to be of childbearing potential unless surgically sterilized by hysterectomy or bilateral tubal ligation/salpingectomy, or post-menopausal for at least two years.

Women of childbearing potential who are sexually active and not using at least 2 medically acceptable method of contraception (e.g. such as implants, injectables, combined oral contraceptives, some intrauterine devices or vasectomized partner for participating females) during the trial and for at least three months after the end of active therapy are not allowed to participate in the trial.

Men will also be counseled on the need to use contraception for all sexual encounters.

5. INVESTIGATIONAL PLAN

5.1. Study Milestones

Registration date: the date the subject signs informed consent.

Eligibility date: the date of the last documented criterion that confirmed subject eligibility.

Enrollment date: the date of initiation of nintedanib treatment.

Treatment discontinuation date: the date the Investigator decides to discontinue the subject from nintedanib treatment for any reason.

5.2. Overall Study Design

This is a single arm, two-stage phase II study designed to evaluate disease control rate in subjects with metastatic appendiceal carcinomas who have had failure of initial fluoropyrimidine-based chemotherapy.

In the first stage, a total of 28 subjects in the evaluable population will be enrolled. Of these, if at least 8 should achieve disease control (Section 13.1.1) the study will continue on to the second stage. In the second stage, 11 participants in the evaluable population (total of 39) will be enrolled. If at least 16 of the 39 total subjects enrolled achieve disease control, then we will be able to reject the null hypothesis. The sample size of evaluable population for both Stage 1 and Stage 2 include participants who begin nintedanib therapy.

Following informed consent and eligibility check, subjects will be enrolled and treated with 200mg of oral nintedanib two times per day and undergo disease evaluation after two months. Subjects who progress will be discontinued from study treatment and those who do not progress will continue twice daily treatment with nintedanib and will continue to undergo disease evaluation every two cycles.

Data from this study will be collected on electronic case report forms (eCRFs) and stored in the clinical trials management system (CTMS).

5.3. Informed Consent

Written informed consent will be obtained from each subject prior to undergoing protocol-specific evaluations or procedures and prior to receiving treatment. In addition, all subjects will provide authorization for the release of their medical records for research purposes.

5.4. Registration/Enrollment/Discontinuation

5.4.1. Subject Registration/Enrollment

Following informed consent, subjects will be registered by the Sponsor and assigned a Study ID number. The Study ID will be a four-digit number sequentially assigned, where 1001 will be the Study ID number assigned to the first registered subject. Following eligibility check per standard operating procedures, eligible subjects will be enrolled on the first date of nintedanib dosing. Study ID numbers assigned to registered subjects not ultimately enrolled will not be re-assigned.

5.4.2. Subject Withdrawal

Subjects are defined as withdrawn from the study if they revoke consent for both treatment and study procedures or the Investigator withdraws them from the study. Subjects **must be** withdrawn from the trial for any of the following reasons:

- Subject withdraws consent from study treatment and study procedures. A subject must be removed from the trial at his/her own request. At any time during the trial and without giving reasons, a subject may decline to participate further. The subject will not suffer any disadvantage as a result.
- Subject is lost to follow-up after three consecutive unsuccessful documented attempts at contacting the subject.
- Development of an intercurrent illness or situation which would, in the judgment of the Investigator, significantly affect assessments of clinical status and trial endpoints.

Subjects may be completely withdrawn from the study by the Investigator if criteria for long-term follow-up described in Section 5.5 are met.

Any subject who withdraws themselves or who is withdrawn from the study by the Investigator will remain under medical supervision until discharge or transfer is medically acceptable.

In all cases, the reason for withdrawal must be documented in the subject's medical records and/or research chart and recorded in the CTMS. Withdrawn subjects are considered to be off-study. Details for the premature termination of the study as a whole are provided in Section 14.2.

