Specimens will be collected according to the schedule in Section 6. Specimens will be collected after subject eligibility confirmation, but prior to administration of the first dose of nintedanib and subsequent cycles. Exploratory biomarker arrays may be used.

Radiology and Tumor Measurements. A computed tomography (CT) scan with oral and intravenous contrast of the chest, abdomen and pelvis will be performed within 28 days prior to the first dose of nintedanib (screening scan). Scans will then be performed within 7 days following anticipated completion of cycle 2 unless clinically proven otherwise and within 7 days of anticipated completion of every two cycles thereafter (e.g. end of cycles 4, 6). A contrast-enhanced MRI of the abdomen and pelvis and a CT scan of the chest without contrast may be substituted if clinically necessary; however, subsequent studies must be performed using the same imaging modality throughout the study period.

For subjects who discontinue study therapy due to toxicity or reasons other than progressive disease, every effort will be made to obtain imaging studies and tumor assessments every 8 weeks (+/- 2 weeks) until documented progression or the start of subsequent anti-cancer therapy.

Subsequent Therapy and Survival Status. Once subjects complete their End of Treatment visit, they will be followed until all treatment-related toxicities have resolved, returned to baseline, stabilized, or are deemed irreversible. Subject's initial anti-cancer therapy following discontinuation of nintedanib treatment and survival

status will be documented.

Subjects (or their family members or designees) may be contacted by telephone, in writing, or during clinic visits after treatment discontinuation for collection of long-term follow-up data approximately every 6 months until death or lost to follow-up, or until the criteria defined for the final analysis (Section 13.3.1) are reached. However, in the event the criteria for the final analysis are met, and there are subjects who have not yet been discontinued from nintedanib treatment, subjects in follow up will continue to be followed until all subjects have discontinued study treatment and completed the safety monitoring period. Long-term follow-up clinical information may also be obtained through chart reviews.

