7.3. Duration of Therapy

In the absence of treatment delays due to adverse event(s), treatment will continue until one of the following criteria applies:

- Disease progression
- Intercurrent illness that prevents further administration of treatment
- Unacceptable adverse event(s)
- Subject decides to withdraw study consent
- General or specific changes in the subject's condition render the subject unacceptable for further treatment in the judgment of the Investigator.

Note: In the event the criteria for the final analysis are met, and there are subjects who have not yet been discontinued from study treatment, they will continue to receive therapy beyond the date the criteria for the study final analysis are met and until one of the above criteria applies.

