13.1.5. Overall Survival

Overall survival is defined as the duration from the start of nintedanib treatment to the date of death from any cause. Subjects who are alive or lost to follow-up at the time of the analysis will be censored at the last known date they were alive.

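### Section 5.4.2 takes ill subjects off study without revoked consent while 5.5 and 7.3 keep following them; PFS, 6-month PFS and OS can be biased upward

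*Combined protocol and SAP*

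**What the plan says.** Section 5.4.2 (Subject Withdrawal) lists three reasons for which a subject has to be "withdrawn from the trial for any of the following reasons". Two are withdrawn consent and loss to follow-up. The third is "Development of an intercurrent illness or situation which would, in the judgment of the Investigator, significantly affect assessments of clinical status and trial endpoints". It needs no revocation of consent. The section closes with "Withdrawn subjects are considered to be off-study".

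Section 7.3 (Duration of Therapy) includes "Intercurrent illness that prevents further administration of treatment" among the criteria that end treatment.

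Section 5.5 (Study Procedures) says: "For subjects who discontinue study therapy due to toxicity or reasons other than progressive disease, every effort will be made to obtain imaging studies", every 8 weeks (± 2 weeks), until progression or new anti-cancer therapy. Footnote f of the study calendar says the same for subjects with disease control. Section 5.5 also provides for collecting "long-term follow-up data approximately every 6 months until death or lost to follow-up, or until the criteria defined for the final analysis" are reached, and adds: "Long-term follow-up clinical information may also be obtained through chart reviews".

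In Section 13, PFS without documented progression is censored at the last radiologic assessment (13.1.3). For OS, subjects alive or lost to follow-up "will be censored at the last known date they were alive" (13.1.5). Both are estimated by Kaplan-Meier (13.3.4.2). Six-month PFS is a binary variable (13.1.4) with no rule for a subject who goes off study before 6 months.

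**The concern.** A subject who becomes seriously ill without documented progression can meet both triggers. Under 7.3 with 5.5, treatment ends and scans and survival contact go on. Under 5.4.2 the subject is off study. Nothing says which governs, and the investigator's judgment decides.

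Kaplan-Meier treats a censored subject as having the same outlook as those still at risk. If subjects leave because of illness and later deaths or progressions are not collected, that assumption is doubtful and the likely error is upward. This is a single-arm trial, so no control arm shares the error. No sensitivity analysis is planned. The disposition summary in 13.3.2 has no category for withdrawal by the investigator, so a reader of the report could not see how often it happened. With 39 subjects, each one is 2.6% of the sample.

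**Working it through.** **1. The sections side by side**

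| | 5.4.2 | 7.3 with 5.5 |
|---|---|---|
| Trigger | Illness or situation that compromises assessment of status and endpoints | Illness that prevents dosing |
| Consent revoked? | Not required | Not required |
| Consequence | Off study | Treatment ends |
| Imaging afterwards | Not stated for off-study subjects | Every 8 weeks until progression or new therapy |
| Survival contact afterwards | Not stated for off-study subjects | About 6-monthly until death, loss to follow-up or final-analysis criteria |

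The triggers differ but overlap; the consequences do not agree. Section 14.1 counts the study complete when all subjects have died and/or withdrawn, which supports reading withdrawal as the end of participation.

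**2. Plan figures.** The plan gives no figure on this point. Its design figures reproduce and are not in dispute. P(reject) = Σ over x = 8 to 28 of P(Bin(28, p) = x) × P(Bin(11, p) ≥ 16 − x), which is 0.0943 at p = 0.30 and 0.9001 at p = 0.50.

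**3. OS illustration (all inputs assumed).** Exponential Kaplan-Meier curve with median 12 months, so h = ln 2 / 12. At month 3 a fraction f of those alive is withdrawn; their later hazard is HR × h, and none of their later deaths is found. Kaplan-Meier then reports S(12) = exp(−12h) = 0.500.

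True S(12) = S(3) × [(1 − f) exp(−9h) + f exp(−9h × HR)]

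S(3) = 0.841. exp(−9h × HR) is 0.595, 0.354, 0.210 and 0.125 for HR = 1, 2, 3 and 4.

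- f = 10%, HR = 3: 0.841 × (0.9 × 0.595 + 0.1 × 0.210) = 0.468, so the estimate is 3.2 points too high.
- f = 5%, HR = 2: excess 0.841 × 0.05 × (0.595 − 0.354) = 0.010.
- f = 15%, HR = 4: excess 0.841 × 0.15 × (0.595 − 0.125) = 0.059.
- HR = 1: excess zero at any f.

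Of 39 subjects, 39 × 0.841 = 32.8 are alive at month 3, so f = 5%, 10% and 15% means about 1.6, 3.3 and 4.9 subjects.

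**4. A second model, for PFS.** Assume a true exponential median of 4 months (h = ln 2 / 4), and a fraction w of all subjects censored 1 month before their event. The hazard that Kaplan-Meier estimates is k × h, with k = (1 − w) / [(1 − w) + w exp(−h × 1)], and exp(−h) = 0.841. True 6-month PFS is exp(−6h) = 0.354.

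- w = 5%: k = 0.95 / (0.95 + 0.042) = 0.958; estimate 0.354^0.958 = 0.37.
- w = 10%: k = 0.90 / (0.90 + 0.084) = 0.915; estimate 0.39.
- w = 15%: k = 0.85 / (0.85 + 0.126) = 0.871; estimate 0.40.

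This model makes every withdrawal precede an event closely, so it leans towards bias by construction.

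**5. Binary 6-month PFS.** Suppose 12 of 39 are known to be alive and progression-free at 6 months and 4 are off study with status unknown. The estimate (95% Clopper-Pearson interval) is 12/39 = 30.8% (17.0% to 47.6%) if they count as failures, 12/35 = 34.3% (19.1% to 52.2%) if they are dropped, and 16/39 = 41.0% (25.6% to 57.9%) if they count as successes. The plan does not say which applies.

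**6. Primary endpoint.** Disease control is binary in everyone who begins nintedanib (13.1.1, 13.2). A subject withdrawn before any qualifying assessment has no qualifying response and is naturally a non-success; one withdrawn after a qualifying assessment already has it.

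**The case against.** The strongest reply is that the documents do not say follow-up ends. Section 5.5 does not list investigator withdrawal as a stopping point and permits chart review, and under 5.3 all subjects authorise release of records for research. A known death counts for OS, and 13.1.3 counts death and investigator-determined progression as PFS events, so decline from the tumour can be recorded as an event rather than censored. This stands in part: handling after withdrawal is unsettled, and the bias is a risk, not a certainty. It does not remove the point, because 5.5 does not say that its procedures apply to off-study subjects, and chart review would not replace scheduled scans.

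Several stronger readings are tempting and go too far.

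- A reader might infer that the trigger is by definition tied to outcome, or that the sickest subjects leave. The text concerns whether subjects can be assessed, and a situation need not be an illness. A link with prognosis is plausible, not stated.
- A reader might take 5.4.2 and 7.3 to give opposite instructions for the same event. The triggers differ. The 7.3 list also includes withdrawal of consent, so appearing there does not by itself mean that follow-up continues; that comes from 5.5.
- A reader might suspect removal of subjects ahead of a bad outcome. Nothing supports this: reasons must be documented and recorded, and 10.1 has retention reviewed regularly.

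The illustrated bias is also modest beside sampling error: the standard error of a 50% rate in 39 subjects is √(0.25/39) = 8.0 points. That bears on priority, but the bias has a direction and costs little to prevent.

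**Conclusion.** The point holds as a conflict between sections and a built-in risk of prognosis-related censoring. The documents do not establish that PFS and OS will be biased. Under the assumptions shown, 12-month OS is 1 to 6 points too high for 5% to 15% of month-3 survivors withdrawn at hazard ratios of 2 to 4, and unbiased at a hazard ratio of 1. The second model gives 6-month Kaplan-Meier PFS about 2 to 5 points too high for 5% to 15% withdrawn. Both assume that nothing is learned after withdrawal. For the binary 6-month rate the direction depends on an unstated rule: dropping unknowns or counting them as successes raises it, and counting them as failures does not. The effect is confined to secondary endpoints, which carry no test or decision rule. The sample size and the 8/28 and 16/39 rules stand.

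**What to change.** Reconcile 5.4.2, 5.5 and 7.3 so that the intercurrent-illness bullet does not by itself end outcome follow-up. Specifically:

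- Separate stopping treatment from leaving outcome follow-up. When treatment stops is for the sponsor to decide and is not part of this point.
- State that subjects who have not revoked consent for follow-up stay in the 5.5 imaging where feasible, and in survival or chart-review follow-up.
- State in 13.1.3 and 13.1.5 that deaths and progressions found this way count as events, subject to the existing rules on subsequent therapy and missed assessments.
- Add to 13.1.4 how subjects with unknown 6-month status are counted.
- Add withdrawal by the investigator, with its reason, to the disposition summary in 13.3.2.

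The cost is wording plus continued scans and contacts, under procedures already in 5.5, for what is likely to be a few subjects. The sample size and decision rule do not change.

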5.4.3. Screen Failures

A subject who, for any reason (i.e. failure to satisfy the eligibility criteria or withdraws consent), terminates his/her study participation before receiving first dose of study therapy is regarded as a “screen failure.” All screen failures will be tracked in the CTMS.

5.5. Study Procedures

Demographics and Medical/Treatment History. Demographics and medical/treatment history will be collected during screening. Medical and treatment history (oncological and relevant non-oncological) will be collected. Cancer history and the following information (including but not limited to) will be obtained:

- Date of first histological/cytological diagnosis
- Prior cancer therapy

All significant medical history findings that occurred prior to the subject signing informed consent will be documented.

Pregnancy Test. A urine or serum pregnancy test will be performed at screening and as clinically indicated for women of childbearing potential.

Women who are pregnant and/or breast-feeding are ineligible for study participation.

Physical Examination. Physical exam by body system, height, weight, body surface area (BSA) and ECOG performance status will be documented during screening and Week 1 of each cycle per Section 6. Height to be assessed at screening only.

Vital Signs. Vital signs will be recorded at screening and Week 1 of each cycle per Section 6 and should include temperature, pulse rate, respiratory rate, blood pressure and oxygen saturation. Blood pressure (only) will be assessed on Day 8 and Day 15 (+/- 2 days) during the first 2 cycles of study treatment. Blood pressure assessment may be done at home by the subject or at another clinic (i.e. local pharmacy) and the

research staff will be responsible for obtaining these results from the subject. Phone contact is acceptable.

Adverse Event Evaluation. All adverse events and serious adverse events will be monitored and documented (regardless of grade or attribution) and reported on an ongoing basis per Section 11. Investigators should refer to the Safety Information section of the current IB for nintedanib. As with any agent, there is always the potential for unexpected AEs, including hypersensitivity reactions.

Concomitant Medications. All medication that is considered necessary for the subject's welfare, and which is not expected to interfere with the evaluation of the study treatment, may be given at the discretion of the Investigator. All medications taken within 2 weeks prior to the enrollment date and during the study must be recorded.

Permitted concomitant therapies include:

- Standard therapies for concurrent medical conditions.
- Supportive care for any underlying illness.
- Palliative radiation therapy is allowed if the target lesion(s) are not included within the radiation field and no more than 10% of the bone marrow is irradiated.
- Granulocyte colony-stimulating factor (G-CSF) and other hematopoietic growth factors may be used in the management of acute toxicity, such as febrile neutropenia, when clinically indicated or at the Investigator's discretion. However, they may not be substituted for a required dose reduction. Subjects are permitted to take chronic erythropoietin.
- Treatment with nonconventional therapies (such as acupuncture), and vitamin/mineral supplements are permitted provided that they do not interfere with the study endpoints, in the opinion of the Investigator.
- Bisphosphonates.
- Subjects taking narrow therapeutic index medications should be monitored proactively (e.g. phenytoin, quinidine, carbamazepine, phenobarbital, cyclosporine, and digoxin).

Laboratory Tests. The blood-based clinical laboratory tests at screening will include a complete blood count with differential and platelets, a comprehensive metabolic panel (including sodium, potassium, chloride, bicarbonate, BUN, creatinine, glucose, and calcium, albumin, alkaline phosphatase, ALT (SGPT), AST (SGOT), total bilirubin, direct bilirubin only if total bilirubin is above normal, and total protein), PTT, PT/INR and urinalysis (UA). After enrollment, a complete blood count with

differential and platelets and a comprehensive metabolic panel (including sodium, potassium, chloride, bicarbonate, BUN, creatinine, glucose, calcium, albumin, alkaline phosphatase, ALT (SGPT), AST (SGOT), total bilirubin, direct bilirubin only if total bilirubin is above normal and total protein) will be performed according to the Study Calendar.

Correlative Studies. Ascites will be removed from the subject when required as a part of standard of care and the entire volume that is removed for clinical purposes and remaining after any diagnostic tests will be processed to concentrate any cells and create a cell block(s) by CHS Pathology. The ascites cell block will be banked and stored at room temperature at the BSR for VEGF levels and for future assays.

Serum (2- 10 ml tubes) specimens from subjects and will be processed within one hour of collection, if possible, but may be kept at 4°C for no longer than 4 hours before processing. Serum will be processed and stored at -80°C until future testing. Specimens will be stored at the CHS Biospecimen Repository.

Specimens will be collected according to the schedule in Section 6. Specimens will be collected after subject eligibility confirmation, but prior to administration of the first dose of nintedanib and subsequent cycles. Exploratory biomarker arrays may be used.

Radiology and Tumor Measurements. A computed tomography (CT) scan with oral and intravenous contrast of the chest, abdomen and pelvis will be performed within 28 days prior to the first dose of nintedanib (screening scan). Scans will then be performed within 7 days following anticipated completion of cycle 2 unless clinically proven otherwise and within 7 days of anticipated completion of every two cycles thereafter (e.g. end of cycles 4, 6). A contrast-enhanced MRI of the abdomen and pelvis and a CT scan of the chest without contrast may be substituted if clinically necessary; however, subsequent studies must be performed using the same imaging modality throughout the study period.

For subjects who discontinue study therapy due to toxicity or reasons other than progressive disease, every effort will be made to obtain imaging studies and tumor assessments every 8 weeks (+/- 2 weeks) until documented progression or the start of subsequent anti-cancer therapy.

Subsequent Therapy and Survival Status. Once subjects complete their End of Treatment visit, they will be followed until all treatment-related toxicities have resolved, returned to baseline, stabilized, or are deemed irreversible. Subject's initial anti-cancer therapy following discontinuation of nintedanib treatment and survival

status will be documented.

Subjects (or their family members or designees) may be contacted by telephone, in writing, or during clinic visits after treatment discontinuation for collection of long-term follow-up data approximately every 6 months until death or lost to follow-up, or until the criteria defined for the final analysis (Section 13.3.1) are reached. However, in the event the criteria for the final analysis are met, and there are subjects who have not yet been discontinued from nintedanib treatment, subjects in follow up will continue to be followed until all subjects have discontinued study treatment and completed the safety monitoring period. Long-term follow-up clinical information may also be obtained through chart reviews.

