1.3. Exploratory Objectives

Exploratory study objectives include:

- Evaluation of serum VEGF,
- Evaluation of ascites VEGF,
- Hypertension
- Frequency of paracentesis in subjects with ascites at study entry

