6. STUDY CALENDAR

Cycle = 28 days (no visit on Week 4)

	Pre-treatment	Clinical Study Treatment						Post-treatment		
	Screening Within 28 days (prior to Cycle 1)	Cycle 1 (+/- 3 days)			Cycle 2 (+/- 3 days)			Remaining Cycles (+/- 3 days)	End of Treatment	Follow-up
Week		W1	W2	W3	W1	W2	W3	W1	Within 30 days of last drug dose	Every 6 months until death , LTF, or completion of long- term follow-up
Informed consent and HIPAA waiver	X									
Demographics	X									
Medical history	X									
Urine or serum pregnancy test ^a	X									
Concurrent medications ^m	X	X			X			X	X	
Physical exam ^{g,m}	X	X ^e			X			X	X	
Vitals ^{h,m}	X	X	X ⁿ	X ⁿ	X	X ⁿ	X ⁿ	X	X	
ECOG performance status ^m	X	X ^e			X			X	X	
Adverse event evaluation ^o	X	Ongoing							X	
CBC w/differential ^m	X	X ^e			X			X	X	
CMP ^{j,m}	X	X ^e			X			X	X	
PTT	X									
PT/INR	X	X ^e								
Urinalysis	X									

Serum for correlative studies ^{b,m}		X			X			X	X	
Ascites for correlative studies ^k		X	X	X	X	X	X	X	X	
Radiologic evaluation by CT and tumor measurements by RECIST 1.1	X						X ^c	X ^d	X	X ^f
Survival status										X ^l
Nintedanib dispensing ⁱ		X			X			X		
Nintedanib compliance assessment					X			X	X	

- a: In women of child-bearing potential; within 7 days of study drug administration and as clinically indicated throughout participation in the study
- b: Serum sample will be collected and assayed for VEGF levels and stored for future study. At the C1D1 timepoint, collect serum after subject eligibility confirmation but prior to first nintedanib dose. At all time-points, serum should be collected prior to nintedanib dosing.
- c: Within 7 days of anticipated completion of cycle 2
- d: Within 7 days of anticipated completion of every two cycles) (e.g. cycles 4, 6, 8)
- e: Not required if screening procedure done w/in 7 days of C1D1 per section 5.5
- f: For subjects with disease control and who discontinue study therapy due to toxicity or reasons other than progressive disease, every effort will be made to obtain imaging studies and tumor assessments every 8 weeks (+/- 2 weeks) until documented progression or the start of new anti-cancer therapy
- g: Physical exam: includes height (at screening only); Weight; body surface area (BSA).
- h: Vitals: temperature; pulse rate; respiratory rate; blood pressure, oxygen saturation

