- i: Nintedanib capsules should be swallowed whole (unopened, uncrushed) with a glass of approximately .8 oz. /240 mL of water. Since subjects will be taking oral nintedanib twice daily, the dose interval should be every 12 hours at the same time every day, usually in the morning and the evening after food intake.
- j: Direct bilirubin required if total bilirubin above normal
- k: Ascites fluid to be collected and assayed for VEGF levels and stored for future study. The decision to remove ascites fluid by paracentesis is determined **as clinically indicated by the investigator** based on subject symptoms. If paracentesis is done as part of standard of care, then every attempt will be made to collect a portion of ascites fluid and store for possible future study
- l: Subject's initial anti-cancer therapy following discontinuation of nintedanib treatment and survival status will be documented.
- m. May be performed within 72 hours of Day 1 of each cycle unless otherwise noted
- n Blood pressure (only) will be assessed on Day 8 and Day 15 (+/- 2 days) during the first 2 cycles of study treatment. Blood pressure assessment may be done at home by the subject or at another clinic (i.e. local pharmacy), and the research staff will be responsible for obtaining these results from the subject. Phone contact is acceptable.
- o. AE evaluation should be performed on Day 8 and Day 15 (+/- 2 days) of Cycles 1 and 2 when the research staff is contacting the subject for BP results.

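### The stated collection window omits ascites removed between consent and eligibility confirmation, and three passages disagree on when ascites may be banked, so a pre-treatment ascites VEGF is left to chance

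*Combined protocol and SAP*

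**What the plan says.** Section 1.3 lists "Evaluation of ascites VEGF" among the exploratory objectives. Section 5.5 (Correlative Studies) ties sampling to clinical care: "Ascites will be removed from the subject when required as a part of standard of care". After describing ascites and serum, it sets the timing for specimens in general: "Specimens will be collected according to the schedule in Section 6", and "Specimens will be collected after subject eligibility confirmation, but prior to administration of the first dose of nintedanib and subsequent cycles".

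In the Section 6 calendar, the row "Ascites for correlative studies" has eight marks: Weeks 1 to 3 of Cycle 1, Weeks 1 to 3 of Cycle 2, Week 1 of the remaining cycles, and End of Treatment. The Screening column, which covers up to 28 days before Cycle 1, is blank in that row. Footnote b gives serum an explicit baseline draw: "At the C1D1 timepoint, collect serum after subject eligibility confirmation but prior to first nintedanib dose". Ascites has only footnote k, which names no dates: "If paracentesis is done as part of standard of care, then every attempt will be made to collect a portion of ascites fluid".

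Under Section 5.1, eligibility is dated by the final criterion to be documented and enrollment by the first dose. Section 13.3.6 plans summaries of expression levels and baseline prevalence, and correlations of the biomarkers with response. Section 13.3.4.2 adds regression of outcomes on correlative biomarkers.

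**The concern.** A window between eligibility confirmation and first dose suits serum, because the study chooses when to draw it. It does not suit a specimen whose timing the study does not control. A consented subject who needs paracentesis before the last eligibility criterion is documented yields fluid that the stated window does not cover. If no further tap is needed before dosing, that subject's first sample is on drug, or there is none.

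The analyses at stake are the baseline summary and the correlation with response. On-treatment fluid comes only from subjects whose ascites persists or returns. Section 2.1 itself cites evidence in ovarian cancer that anti-VEGF therapy reduces ascites. If nintedanib acts similarly, subjects who benefit will tend to stop supplying fluid, and a correlation built on on-treatment samples would be distorted by that selection. A baseline that was never banked cannot be recovered in the analysis.

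**Working it through.** The plan gives no expected number of ascites samples, so there is no figure of its own to reproduce. The check has two parts.

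**1. The passages side by side**

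| Ascites removed | Section 5.5 timing rule | Calendar, ascites row | Footnote k |
|---|---|---|---|
| After consent, before eligibility confirmed | Not covered | No mark | No time limit |
| After eligibility confirmed, before Cycle 1 Week 1 | Permitted | No mark | No time limit |
| Weeks 2 and 3 of Cycles 1 and 2 | Does not fit a rule set before the first dose and before later cycles | Marked | No time limit |

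The three sources do not agree on any of these rows. On the 5.5 wording, a pre-treatment sample requires a tap between eligibility confirmation and first dose.

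**2. Illustrative size**

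The documents do not give the share of subjects with ascites, the interval between taps, or the time from eligibility (or consent) to first dose. All of these are assumptions. Let w be the days available for banking before the first dose and T the tap interval in days. The chance that a subject with ascites has at least one tap in the window is:

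- evenly spaced taps: min(1, w/T)
- randomly timed taps with mean interval T: 1 − exp(−w/T)

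| T | w = 3 (eligibility to dose) | w = 7 (eligibility to dose) | w = 14 (consent to dose) |
|---|---|---|---|
| 7 days, even / random | 3/7 = 43% / 35% | 7/7 = 100% / 63% | 100% / 86% |
| 14 days, even / random | 3/14 = 21% / 19% | 7/14 = 50% / 39% | 14/14 = 100% / 63% |
| 28 days, even / random | 3/28 = 11% / 10% | 7/28 = 25% / 22% | 14/28 = 50% / 39% |

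For counts, take the maximum of 39 subjects (Section 13.1), assume 40% have ascites (39 × 0.40 = 15.6), and use random timing with T = 14:

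- w = 3: 15.6 × (1 − exp(−3/14)) = 3.0 subjects
- w = 7: 15.6 × (1 − exp(−7/14)) = 6.1
- w = 14: 15.6 × (1 − exp(−14/14)) = 9.9
- w = 28 (the full screening window, an upper limit): 15.6 × (1 − exp(−28/14)) = 13.5

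Over ascites shares of 20–60% and mean intervals of 7–56 days, the expected count runs from 0.4 to 8.2 for w = 3, from 0.9 to 14.8 for w = 7, and from 3.1 to 23.0 for w = 28. The direction is the same throughout, but the size depends heavily on the assumptions.

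**The case against.** The best reply is that the 5.5 sentence is a loosely drafted serum rule. Footnote b repeats it almost exactly for serum alone, and read literally for ascites it would exclude the Week 2 and Week 3 samples that the calendar schedules. Footnote k is the only ascites-specific collection note in the calendar. It has no time limit, and 5.5 elsewhere says that all clinically removed fluid left after diagnostics will be processed. On that reading a site could bank screening fluid already. Waiting for eligibility is also defensible, because it avoids holding research specimens from screen failures. Finally, ascites VEGF is exploratory and opportunistic, and no decision rests on it.

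Much of this stands, and it rules out three stronger readings that a reader might infer:

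- **That all fluid from the 28-day screening period is lost or discarded.** No passage says so. Section 5.5 permits collection once eligibility is confirmed, which can fall within screening, and footnote k can be read to cover the rest.
- **That few subjects will have a pre-treatment sample.** No document figure supports this. With a gap of a week and frequent taps, the yield could be substantial.
- **That no baseline level could be derived.** Any tap between eligibility and first dose supplies one. Nor does any passage plan a change from baseline in ascites VEGF.

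The reply does not remove the conflict. Footnote k annotates a row with no Screening mark, and 5.5 states a start point for specimens without exempting ascites. Sites could reasonably follow different passages, and either reading calls for the same correction.

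**Conclusion.** The point holds as a gap and an inconsistency in the collection rules. Fluid taken between consent and eligibility confirmation is outside the window stated in Section 5.5. The calendar schedules no ascites at screening, footnote k is open-ended, and the three need to be reconciled. As written, a pre-treatment ascites VEGF depends on when a clinically driven tap happens to fall.

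On the middle assumption of a 14-day tap interval, banking over 14 days from consent raises the share of subjects with ascites who have a pre-dose sample from 21% to 100% with evenly spaced taps, or from 19% to 63% with random timing, if the eligibility-to-dose gap is 3 days. With a 7-day gap the starting points are 50% and 39%. These are illustrations, not estimates from the documents.

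The effect is confined to the exploratory analyses in Section 13.3.6 and the biomarker regressions in Section 13.3.4.2. The primary endpoint and the sample size are unaffected. The change is worth making because fluid not banked cannot be recovered and the cost is small.

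**What to change.** - In Section 5.5, give ascites its own window: bank fluid from any standard-of-care paracentesis from signed consent onward. Keep the post-eligibility, pre-dose window for serum.
- In Section 6, add a Screening mark to the ascites row and word footnote k to match the new window, including the mid-cycle marks.
- Define the baseline ascites VEGF as the last sample before the first dose.
- In Section 13.3.6, base the correlation with response on that baseline sample. Report on-treatment fluid separately, noting that it comes only from subjects whose ascites persists.

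This adds no procedure. The decision to perform paracentesis stays clinical, the fluid is already being removed, Section 5.3 places consent before protocol procedures, and Section 5.4.1 assigns a Study ID at registration, so specimens can be labelled. The cost is a sentence or two, one calendar cell, consent wording to match if it does not already cover this, and a few banked specimens from subjects who then fail screening. One limit remains: only subjects who need a tap between consent and first dose will have a baseline, so the report should state how many of those with ascites contributed.
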